8.4.2.1.2 Causality

Causality (likelihood that the event is caused by the study agents) will be assessed by the principal investigator or designee considering the factors listed under the following categories:

Definitely Related

- reasonable temporal relationship
- follows a known response pattern
- clear evidence to suggest a causal relationship
- there is no alternative etiology

Probably Related

- reasonable temporal relationship
- follows a suspected response pattern (based on similar agents)
- no evidence of a more likely alternative etiology

Possibly Related

- reasonable temporal relationship
- little evidence for a more likely alternative etiology

Unlikely Related

- does not have a reasonable temporal relationship
AND/OR
- there is good evidence for a more likely alternative etiology

Not Related

- does not have a temporal relationship
AND/OR
- definitely due to an alternative etiology

Note: Other factors (e.g., dechallenge, rechallenge, if applicable) should also be considered for each causality category when appropriate. Causality assessment is based on available information at the time of the assessment of the AE. The investigator may revise the causality assessment as additional information becomes available.

Causality assessment will be reviewed by the sponsor. The sponsor may make a separate and final determination on the “reasonable possibility” that the event was “related” (comprising definitely, probably, and possibly related) or “unrelated” (comprising unlikely and not related) to the study agent, in keeping with applicable (US FDA) guidance on sponsor IND safety reporting.

8.4.2.2 Recording of Events

AEs will be promptly recorded in the research database, regardless of possible relationship to study interventions. If a diagnosis is clinically evident (or subsequently determined), the diagnosis rather than the individual signs and symptoms or laboratory abnormalities will be recorded as the AE. The investigator will review events regularly to ensure they have been captured correctly and to perform assessment of events individually and cumulatively to assess possible safety trends.

8.4.2.3 Investigator Reporting Responsibilities

The principal investigators and/or equally qualified designees will check daily for events that may require expedited reporting.

The principal investigators and/or equally qualified designees will also monitor all accumulating data no less than weekly, or according to superseding NIH or NIAID policy, whichever is more frequent.

Data will be reviewed by the principal investigators/designees on a regular basis for accuracy and completeness.

Data will be submitted to the sponsor in keeping with all applicable agreements and when requested, such as for periodic safety assessments, review of IND annual reports, review of IND safety reports, and preparation of final study reports.

The principal investigators and/or other study designee will ensure prompt reporting to safety oversight bodies (e.g., CSO, DSMB), regulatory entities, and stakeholders as specified below, and according to any additional requirements or agreements.

8.4.2.3.1 Adverse Events

Unless otherwise specified above, AE data will be entered into the research database no less than every other week and will include all data through 1 week prior to database entry.

8.4.2.3.2 Serious Adverse Events (Expedited Reporting)

Unless otherwise specified above, all SAEs (regardless of relationship and whether or not they are also UPs) must be reported to the CSO as specified by the CSO (e.g., Research Electronic Data Capture [REDCap] system; use the Safety Expedited Report Form [SERF]/email if REDCap is not available). If the preferred/indicated mechanism for reporting is not available, the CSO/SMM should be contacted by telephone, fax, or other reasonable mechanism to avoid delays in reporting.

CSO CONTACT INFORMATION:

Clinical Safety Office
[name]
[name]
[contact]
[contact]
Email: [contact]
REDCap: <https://crimsonredcap.cc.nih.gov/redcap/index.php>

Unless otherwise specified above, deaths and immediately life-threatening SAEs must be reported to the CSO promptly, and no later than the **first business day** following the day of study personnel awareness.

All other SAEs must be reported to the CSO no later than the **third business day** following the day of study personnel awareness.

If an individual subject experiences multiple SAEs in a closely timed/overlapping “cause-and-effect” (cascade) sequence, the principal investigators, after careful evaluation, will report ONLY primary/precipitating event(s) individually. SAEs that are determined to be definitely secondary to other SAEs will be detailed in the narrative portion of the report of the relevant primary/precipitating SAE. A clinical rationale and findings to support such reporting should be part of the narrative.

For each SAE report, the research database entry MUST match the corresponding entries on the SAE report (e.g., start and stop dates, event type, relationship, and grade), and **must be updated if necessary** (e.g., if the SAE report was generated after the corresponding AE was entered in the research database).

Unless otherwise specified above, SAEs that have not resolved by the end of the per-protocol follow-up period for the subject are to be followed until final outcome is known (to the degree permitted by the EC-approved informed consent form). If it is not possible to obtain a final outcome for an SAE (e.g., the subject is lost to follow-up), and to update the CSO, the last known status and the reason a final outcome could not be obtained will be recorded by the investigator on an SAE report update and the CRF.

8.4.2.3.3 Unanticipated Problems

Unless otherwise specified above, UPs (as defined in this protocol, or as defined by the EC of record, whichever definition is more conservative) that are also AEs or SAEs, must be reported to the CSO (by REDCap, or by email and SERF if REDCap is not available) no later than when they are due to be reported to the EC.

UPnonAEs are NOT reported to the CSO but must be reported to the Clinical Trials Management (CTM) group according to their requirements and preferred methods. If the UPnonAE raises a significant potential subject safety concern, the SMM should be consulted by email or phone no later than when reports are made to the CTM.

8.4.2.3.4 Pregnancy

Unless otherwise specified above, all pregnancies will be reported (by REDCap, or by email and SERF if REDCap is not available) to the CSO no later than the first business day following the day of study personnel awareness.

Pregnancy outcome data (e.g., delivery outcome, spontaneous or elective termination of the pregnancy) will be reported to the CSO no later than the third business day following the day of study personnel awareness (by REDCap, or by email and SERF if REDCap is not available).

Pregnancy itself is not an AE. Events that meet AE or SAE criteria in relation to pregnancy, delivery, or the conceptus/neonate (see section [8.4.1](#)) are reportable (by REDCap, or by email and SERF if REDCap is not available).

In the event of pregnancy in a study subject exposed to study agent, the following actions will be taken, with the goal of ensuring maternal and fetal well-being, in consultation with the SMM, independent safety monitor (ISM), and DSMB:

- Sample collection will continue per guidelines below:
 - Only proceed with blood draw if subject's hemoglobin value is ≥ 8.0 gm/dL (assessed via finger prick).
 - PK samples (4 mL) will be collected according to the regular study schedule (Day 1, Day 7, Day 14, Day 28, Day 56, Day 84, Day 112, Day 140 and Day 168).

- The finger prick used to measure hemoglobin at the visits specified above will also be used to collect blood smears for detection of Pf infection by microscopic examination, and dried blood spots for Pf RT-PCR. A venipuncture (up to 0.5 mL) may also be performed if the investigators believe that a finger prick would not provide a sufficient volume of blood to prepare dried blood spots for the Pf RT-PCR assay.
- Serum storage samples will not be drawn if a subject becomes pregnant.
- Continue to follow for safety for the duration of the pregnancy and for a period of up to 12 months (per investigator discretion) following delivery for assessment of the neonate (see [Appendix C](#)).
- Request to unblind the subject, if applicable, AND if doing so would offer a benefit to the subject.
- Report, no later than the first business day after study personnel awareness, to the ISM and DSMB.
- Advise subject to notify the obstetrician of study participation and study agent exposure, providing contact information for the obstetrician to contact the study principal investigator, should this be required, and with the subject's consent.

8.4.2.4 Sponsor's Reporting Responsibilities

Events reported to the sponsor will be promptly evaluated and will be reported as required according to FDA IND safety reporting guidance and regulations. IND safety reports will be sent to other investigators conducting research under the same IND and will be shared with other stakeholders according to applicable agreements.

The sponsor will also submit an IND annual report of the progress of the investigation to the FDA as defined in 21 CFR 312.33.

All UPs will be evaluated by the sponsor, and a summary of the event, and any necessary (corrective/preventative) actions, will be distributed to investigators conducting research under the same IND as may be relevant and appropriate.

8.4.3 Withdrawal Criteria for an Individual Subject

An individual subject will be withdrawn from the study for any of the following:

- An individual subject's decision. (The investigator should attempt to determine the reason for the subject's decision.)
- Non-compliance with study procedures to the extent that it is potentially harmful to the subject or to the integrity of the study data.
- A change in the subject's condition as follows:
 - Loss of the ability to provide informed consent.
 - Withdraws permission to have data stored for future research.
- The investigator determines that continued participation in the study would not be in the best interest of the subject.

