6 STUDY INTERVENTION

6.1 STUDY INTERVENTION ADMINISTRATION

6.1.1 Study Intervention Description

The study intervention involves a single administration of L9LS or placebo to each subject. All study agent administration will take place at the Kalifabougou study site.

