7 STUDY INTERVENTION DISCONTINUATION AND PARTICIPANT DISCONTINUATION/WITHDRAWAL

7.1 DISCONTINUATION OF STUDY INTERVENTION

Study intervention may be discontinued for a protocol-defined group or arm (i.e., pausing), or it may be discontinued for all subjects and enrollment suspended (i.e., halting). Pausing and halting are described in sections [8.4.5](#) and [8.4.6](#). Subjects who have already received the study agent at the time of a pause or halt will continue planned follow-up under the protocol.

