8.4.3.2 Replacement of Withdrawn Subjects or Subjects Who Discontinue Study Agent

Subjects withdrawn prior to study agent administration will be replaced.

All subjects exposed to study agents MUST be included in the safety dataset.

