Samples and data acquired under this protocol will be tracked using BSI Systems software. Any loss or unanticipated destruction of samples (for example, due to freezer malfunction) or data (for example, misplacing a printout of data with identifiers) that meets the definition of a reportable event will be reported to the FMOS/FAPH EC.

Additionally, subjects may decide at any point not to have their samples stored. In this case, the principal investigator will destroy all known remaining samples and report what was done to both the subject and to the EC. This decision will not affect the individual's participation in this protocol or any other protocols at NIH.

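### Section 8.4.3 ends follow-up of already dosed participants who refuse future data storage or whose non-compliance threatens data integrity, although no treatment remains to be stopped

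*Combined protocol and SAP*

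**What the plan says.** Section 8.4.3 opens with a mandatory rule: "An individual subject will be withdrawn from the study for any of the following". Two of its criteria matter here. One applies when the participant "Withdraws permission to have data stored for future research"; it is listed under changes in the participant's condition. The other is "Non-compliance with study procedures to the extent that it is potentially harmful to the subject or to the integrity of the study data". Neither distinguishes participants before dosing from participants after it.

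Section 6.1.1 states: "The study intervention involves a single administration of L9LS or placebo to each subject". Section 8.4.3.2 replaces only those withdrawn before dosing, and adds: "All subjects exposed to study agents MUST be included in the safety dataset". Section 7.2 encourages, but does not require, one early termination visit.

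Other sections keep comparable participants in the study:

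- Section 10.3: "subjects may decide at any point not to have their samples stored", and that choice does not affect "participation in this protocol or any other protocols at NIH".
- Section 7.1: "Subjects who have already received the study agent at the time of a pause or halt will continue planned follow-up under the protocol".
- Section 7.3: two consecutive missed visits, or three in total, are protocol deviations. A participant whose missed visit cannot be rescheduled may go on to the next one.
- Section 8.4.2.3.4: a participant who becomes pregnant after dosing keeps PK, smear, RT-PCR and safety follow-up.

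**The concern.** Withdrawal criteria usually protect participants from further exposure. Here exposure is complete on day 0, so withdrawal afterwards removes information and nothing else.

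Three things are at stake. First, the primary efficacy analysis (section 9.4.4) is MITT on time to first infection, so a participant withdrawn while uninfected becomes a censored observation. If the non-compliance is related to illness or infection, that censoring is informative. Second, monthly pregnancy testing and routine safety visits stop. Table 2 then captures only related SAEs that staff happen to learn of. Third, the line between a deviation that is recorded and non-compliance that forces withdrawal is left to judgement, so sites may draw it differently.

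**Working it through.** **1. The passages side by side**

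| Situation of a dosed participant | Section | Follow-up |
|---|---|---|
| Refuses storage of samples | 10.3 | Continues |
| Refuses storage of data for future research | 8.4.3 | Ends |
| Misses two visits in a row, or three in total | 7.3 | Deviation; may continue |
| Non-compliance judged potentially harmful to data integrity | 8.4.3 | Ends |
| Dosing paused or halted | 7.1 | Continues |
| Becomes pregnant | 8.4.2.3.4 | Continues, with limits on blood draws |

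Inclusion criterion 6 (section 5.1) requires willingness to store both samples and data. It therefore does not explain why refusing one ends participation and refusing the other does not.

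**2. What one withdrawal costs**

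Scheduled smears in the efficacy window of section 4.1 (from two weeks) fall on days 14, 21, 28, 42, 56, 70, 84, 98, 112, 126, 140, 154 and 168. That is 13 visits, the maximum one participant can lose. One placebo recipient is 1/72 = 1.4% of the arm. If the female weight strata fill to 64 and 3:1 allocation holds in each, a stratum has 64/4 = 16 placebo recipients, and one is 1/16 = 6.3%.

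The documents give no rate. If 1% to 5% of 288 were withdrawn this way (assumption), that is 2.9 to 14.4, or about 3 to 14 participants. This is an upper bound on lost endpoints, because anyone infected before withdrawal keeps the event.

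**3. Power**

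The plan's own figure comes first. Table 4, first row, has 72 per arm, placebo risk p0 = 0.5, efficacy 0.6, 10% dropout and two-sided 0.05.

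- p1 = 0.5 × (1 − 0.6) = 0.2
- HR = ln(0.8)/ln(0.5) = 0.322, so |ln HR| = 1.134
- Events: 0.9 × 72 × 0.5 = 32.4 and 0.9 × 72 × 0.2 = 12.96
- Power = Φ(1.134/√(1/32.4 + 1/12.96) − 1.96) = Φ(1.49) = 93.2%, against 93% stated

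The same formula comes within 2 points of 26 of the 27 rows. The exception is 40 per arm at 0.5 and 0.8 (93 stated, 90.4 computed).

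With p0 = 0.5 and efficacy 0.6, and total loss assumed to rise:

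| Comparison | 10% | 15% | 20% |
|---|---|---|---|
| 216 vs 72 (primary) | 99.7% | 99.6% | 99.4% |
| 72 vs 72 | 93.2% | 91.8% | 90.2% |
| 48 vs 48 | 80.4% | 78.1% | 75.6% |

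**4. Direction of a possible bias**

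This is a deliberately crude illustration on the risk-ratio scale of section 9.2.2, not the hazard-ratio scale of the primary analysis. Let a fraction w of one arm be withdrawn before any detected infection, with 24-week risk q had they stayed. The observed risk in that arm is then (p − w·q)/(1 − w). True values are p0 = 0.5, p1 = 0.2, efficacy 0.6.

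| Loss confined to | q | w = 2% | w = 5% |
|---|---|---|---|
| L9LS | 0.5 | 0.612 | 0.632 |
| L9LS | 1 | 0.633 | 0.684 |
| Placebo | 1 | 0.592 | 0.578 |

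Example for L9LS, q = 1, w = 5%: (0.2 − 0.05)/0.95 = 0.158, and 1 − 0.158/0.5 = 0.684. Example for placebo, w = 5%: (0.5 − 0.05)/0.95 = 0.474, and 1 − 0.2/0.474 = 0.578.

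**5. What the analysis plan would do with such losses**

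Section 9.4.1 treats missingness below about 10% as completely at random, without examining that assumption. Its two sensitivity analyses impute missing binary observations. Section 9.4.4 specifies no analysis for informative censoring in the time-to-infection model.

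**The case against.** The best defence is that the rule is narrower, and its consequences smaller, than they look. Four stronger readings are tempting, and the documents do not support them.

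- *Withdrawn participants' data are thrown away.* They are not. Section 8.4.3.2 keeps every exposed participant in the safety dataset, and the MITT set (section 9.3) does not require completion. Only later follow-up is missing. The primary safety endpoint covers 7 days, so it is affected only by withdrawal in the first week.
- *Refusing data storage is related to outcome.* Nothing in the documents suggests this. The informative-censoring argument rests on non-compliance alone.
- *Missing visits or taking an antimalarial forces withdrawal.* Section 7.3 already has a rule for missed visits under which participants may continue. Section 6.5 allows antimalarials with investigator approval, and section 8.2.1 ties malaria treatment to symptoms with a positive smear, so the infection would normally be recorded first. Unapproved self-treatment remains, and no section says it triggers withdrawal.
- *The bias would flatter L9LS.* Symptom-driven loss would be expected more on placebo, and that tends to lower apparent efficacy.

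It is also fair that section 10.3 concerns samples and not data, that section 7.1 concerns pausing the intervention and not a participant's own choice, and that section 8.4.2.3.2 follows unresolved SAEs to outcome.

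All of this stands, and it limits the point. It does not explain why follow-up should end once the only dose has been given, or why data and samples are treated differently when the entry criterion covers both.

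**Conclusion.** The point holds in a limited form. Section 8.4.3 requires withdrawal of dosed participants for two reasons that call for no change in treatment, and so gives up later smear, RT-PCR, PK and safety data that could have been collected. The storage criterion is inconsistent with section 10.3; the non-compliance criterion sits badly with section 7.3.

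The size is modest. The effect on primary power is negligible, and the small female weight strata are the most exposed. Bias through non-compliance is possible but not shown. In the illustration, 2% to 5% loss moves an efficacy of 0.60 to between 0.61 and 0.68 if confined to L9LS, and down to between 0.58 and 0.59 if confined to placebo. Those figures rest on assumed rates and on extreme assumptions about who is lost.

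**What to change.** In section 8.4.3, for participants who have received the study agent:

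1. Treat withdrawal of permission for future data storage as ending future-use storage only, and continue scheduled follow-up. Reconcile the text with section 10.3.
2. For non-compliance that affects only data integrity, record a protocol deviation and continue scheduled smears and safety visits unless the participant withdraws consent. Reconcile the text with section 7.3.

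Leave unchanged the harm-to-participant part of the non-compliance criterion, the participant's own decision, loss of capacity to consent, and the investigator's best-interest criterion.

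The cost is a change to protocol and consent wording. The downside is that sites keep scheduling visits for poorly compliant participants.

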8.4.3.1 Re-enrollment and Unplanned Procedure Repetition

Unless otherwise specified within this protocol (e.g., rescreening as described in section 5.5), each person who is a subject in this study may be enrolled and may pass through each step and process outlined in the protocol, only **ONCE** (i.e., subjects may not “go back” and repeat a protocol step already completed).

8.4.3.2 Replacement of Withdrawn Subjects or Subjects Who Discontinue Study Agent

Subjects withdrawn prior to study agent administration will be replaced.

All subjects exposed to study agents MUST be included in the safety dataset.

8.4.4 Additional Safety Oversight

8.4.4.1 Safety Review and Communications Plan

A safety review and communication plan (SRCP) is required for this protocol. The SRCP is an internal communications document between the principal investigators and the CSO, as sponsor representative, which delineates key safety oversight responsibilities of the principal investigators, the CSO, and other stakeholders. The SRCP includes a plan for conducting periodic safety surveillance assessments by the CSO.

8.4.4.2 Sponsor Medical Monitor

A SMM, representing the sponsor, has been appointed for oversight of safety in this clinical study. The SMM will be responsible for performing safety assessments as outlined in the SRCP.

8.4.4.3 Oversight Committees

8.4.4.3.1 Independent Safety Monitor in Mali

The ISM is an expert who does not have direct involvement in the conduct of the study and has no significant conflicts of interest as defined by NIAID policy. An ISM in Mali will review the study prior to initiation and will be available to advise the investigators on study-related medical issues and act as a representative for the welfare of the subjects. The ISM will conduct independent safety monitoring. The ISM is an expert in the field of oversight of clinical trials conducted in Mali and internal medicine, specifically in the population under study in Mali.

All deaths, SAEs, UPs, pregnancies, and FDA IND safety reports will be reported by the principal investigators to the ISM prior to or at the same time they are submitted to the EC or CSO unless otherwise specified herein. The ISM will be notified immediately if any pausing rule is met. The principal investigators will also notify the ISM if intentional or unintentional unblinding occurs. The ISM will have access to blinded data only. If the ISM is unblinded to the study agent given to an individual subject during medical management, the ISM will report that unblinding to the DSMB Executive Secretary.

8.4.4.3.2 Data and Safety Monitoring Board

The NIAID intramural DSMB includes independent experts that do not have direct involvement in the conduct of the study and have no significant conflicts of interest as defined by NIAID policy. The DSMB may include an *ad hoc* member from the host country, as needed. The DSMB will review the study protocol, consent documents, and investigator brochure prior to initiation and twice a year thereafter, or as may be determined by the DSMB.

The DSMB may convene additional reviews as necessary. The DSMB will review the study data as needed to evaluate the safety, efficacy, study progress, and conduct of the study.

All deaths, SAEs, UPs, pregnancies, and IND safety reports will be reported to the DSMB at the same time they are submitted to the EC and CSO unless otherwise specified herein.

All cases of intentional or unintentional unblinding will be reported to the DSMB not later than 1 business day from the time of study personnel awareness.

The principal investigators will notify the DSMB at the time pausing or halting criteria are met and obtain a recommendation concerning continuation, modification, or termination of the study.

